
cost of surgery and aftercare in surgical patients, we believe that this project will establish the ground-work necessary to develop a sustainable clinical program for other surgical practices to minimize post-surgical complications and overall costs.

2. Objectives (include all primary and secondary objectives)

1. Evaluate whether an intensive pre- post-surgical smoking cessation intervention will promote smoking cessation both pre- and post-surgery.

Hypothesis: An intensive smoking intervention will promote smoking abstinence across the pre- and post-surgical phases. Secondary outcomes will include cessation at 1-month postsurgical follow up and other smoking-related outcomes (withdrawal, craving).

2. Assess whether changes in smoking are associated with surgical recovery outcomes.

Hypothesis: Patients who show longer periods of sustained smoking abstinence pre- and post-surgery will have better recovery post-surgery as evidenced by the following outcomes: shorter length of stay, fewer admissions to the ICU, lower total cost of procedure, smaller total quantity of opioid analgesic use, and lower 30-day hospital readmission rates.

3. Examine baseline decision-making characteristics, including smoking motivation, delayed discounting, and distress tolerance, as predictors of post-surgical recovery and smoking cessation outcomes.

Hypotheses: (1) Patients with strongest positive and negative reinforcement-based smoking motives (i.e., patients whose motives to smoke center around experiencing the positive outcomes of smoking, such as mood enhancement and/or ameliorating the cons of abstaining from smoking, including craving and negative affect) will be most likely to resume smoking post-surgery. (2) Patients with steeper discounting curves at study baseline and/or lower distress tolerance will be less likely to abstain from smoking pre-surgery, may request higher quantities of opioid analgesics post-surgery, and will be at the greatest risk of relapsing to smoking post-surgery.

The overall objective of this study is to assess the feasibility of conducting a pre-postoperative smoking cessation study in presurgical patients. If a positive signal is found, then these data will be used to support a large-scale grant application to evaluate this approach using a randomized, controlled study design.

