5. Study Procedures

- a. Study design, including the sequence and timing of study procedures (distinguish research procedures from those that are part of routine care).

In this two-year open-label feasibility study, 20 smokers who are planning to undergo elective surgery will complete a 12-week intensive pre- post-surgical smoking cessation intervention, involving three major components: (1) varenicline administration, (2) standardized smoking cessation counseling, and, during the pre-surgery phase, (3) incentives for urine samples that test negative for cotinine. Upon verifying that all study eligibility criteria are met, patients will enter the intervention phase of this study. During this phase, patients will attend weekly study visits to receive the pre-surgical component of the intensive smoking cessation intervention in approximately the 4-6 weeks leading up to surgery, and complete approximately six additional weekly study visits post-surgery in order to continue with the post-surgical varenicline administration component of the intensive smoking intervention for a total of 12 weeks, and to allow for in-person assessment of post-surgical smoking cessation and surgical recovery outcomes. Finally, participants will be scheduled for an in-person follow-up visit approximately one month following completion of the study to assess study outcomes. In some cases, this follow-up period may extend as long as six months to collect data that ensures study outcomes are being met.

Recruitment: We will recruit participants via physician or self-referrals. A number of strategies may be utilized to identify potential participants early in the elective surgical process. We will provide medical departments and physicians detailed information about study eligibility criteria and procedures and encourage them to provide potentially eligible patients with information to contact the study team. We will also post flyer advertising a smoking cessation study for elective surgical patients in common areas and waiting rooms to enable potential participants to contact us directly. All interested individuals will be instructed to call the study team and complete a brief phone screen to establish initial study eligibility before conducting a full screening visit.

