There is no standard and/or routine access to smoking cessation in elective surgical patients. This study will not disrupt any ongoing routine care associated with the participant's surgery.

- e. Justification for inclusion of a placebo or non-treatment group.

N/A

- f. Definition of treatment failure or participant removal criteria.

Participants failing to continue to meet any of the inclusion/exclusion criteria will be removed from the study and an appropriate clinical referral provided. For example, subjects developing a psychiatric disorder or symptoms requiring treatment (e.g., mania, suicidality, and psychosis), major medical illnesses or serious injuries, which would preclude further participation, will be withdrawn. Subjects who consistently fail to show up for the first treatment session may also be withdrawn.

- g. Description of what happens to participants receiving therapy when study ends or if a participant's participation in the study ends prematurely.

Participants will be debriefed after completing the 1-month follow-up, 6-month follow-up, or premature removal. They will be fully informed about all treatment options for smoking cessation and provided with additional referrals as needed. Any participant who is discharged or voluntarily leaves the study will be provided referrals for obtaining assistance with smoking cessation. The participants will continue meeting with their surgical team, consistent with routine practice for post-surgical patient care and independent of the study.

6. Inclusion/Exclusion Criteria

Inclusion Criteria: We will recruit cigarette smokers who have scheduled an elective surgery to participate in the study. Inclusion criteria will include having a surgery scheduled 5-10 weeks in advance, reporting regular cigarette smoking (smoking 3 times a week or more) and providing a cotinine-positive urine sample.

Exclusion Criteria: Exclusion criteria will include being contraindicated for varenicline use, using products other than cigarettes as a primary nicotine product (including e-cigarettes), providing an illicit drug-positive urinalysis test without evidence of concurrent prescription (e.g., for narcotic pain medications, for example), being pregnant or breastfeeding, or a score >20 on the Beck Depression Inventory-II or a score ≥ 0 on the suicide question of the BDI, past year suicidal ideations or behavior on the C-SSRS, being

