- b. Justification and safety information if FDA approved drugs will be administered for non-FDA approved indications or if doses or routes of administration or participant populations are changed.

N/A

- c. Justification and safety information if non-FDA approved drugs without an IND will be administered.

N/A

8. Study Statistics

Outcome Measures: We will collect a variety of outcome measures to enable a full characterization of decision-making factors at baseline, and the impact of this intervention on smoking status, postsurgical outcomes, opioid analgesia utilization, and cost.

- a. Primary outcome variable.

Smoking Outcomes: Our primary outcome variable will be smoking status. Smoking abstinence will be defined as a negative biochemical sample + self-report of no smoking for the past 7 days, mean % negative samples, and mean continuous negative samples. Smoking will be evaluated within each pre and post-surgical phase, and collapsed over the 11-week targeted cessation period (following the TQD during week 2). Point prevalence smoking abstinence at the follow-up will be defined as a negative cotinine sample + self-report of no smoking for the past 7-days.

b. Secondary outcome variables.

Secondary smoking outcomes will include ratings of nicotine withdrawal and craving, using standardized measures, and frequency of adverse events judged to be related to varenicline or smoking cessation.

Surgical Recovery Outcomes: A variety of postsurgical outcomes will be evaluated. These will include length of hospital stay, overall quantity and frequency of opioid analgesic use, pain ratings of during the recovery period, types and frequency of post-operative complications, frequency of admission into the intensive care unit, and 30-day hospital readmission rates.

c. Statistical plan including sample size justification and interim data analysis.

Since this is an open-label study design, results will be analyzed in a mostly descriptive method.

Smoking Outcomes: Smoking outcomes will be evaluated as a function of time over the 11-week intervention. Smoking cessation rates will also be compared from the pre to post-intervention phases.

Surgical Recovery Outcomes: Surgical outcomes will be evaluated as a function of percent biochemically-confirmed smoking abstinence, to assess whether the duration and/or magnitude of smoking abstinence is statistically associated with 30-day readmission rates, opioid analgesic use, and other surgical outcomes.

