Study-related Measures: We will generate summary scores for each of the study measures and evaluate whether baseline values were positively associated with smoking outcome, and whether there were any changes in measures over time as a function of smoking status. These data will be used to help identify which measures may be most sensitive to change over time for a full-scale trial.

Sample Size Considerations: Our proposed sample of 20 completers is consistent with other open label studies of this kind. Additionally, our pilot data on bariatric patients from FY 2014 included only 23 smokers and still provided enough power to show a signal regarding the effects of smoking status on duration of hospital stay, total costs, and 30-day hospital readmissions. As such, we believe 20 completers will be a large enough sample to demonstrate an effect of the intensive intervention on promoting smoking cessation and minimizing post-surgical complications, and will also be a feasible sample size to recruit within the 2-year study period.

d. Early stopping rules.

This study will be stopped if we have evidence that enrolling participants into the study puts them at undue risk of experiencing complications during their surgery. We do not anticipate this happening, however since this is the first study of its kind in this population, we will monitor the data closely to verify safety of the participants.

9. Risks

a. Medical risks, listing all procedures, their major and minor risks and expected frequency.

Varenicline Administration:

Side-effect risks associated with varenicline administration (21): Allergic reactions to varenicline can be life-threatening and are generally characterized by a swelling of the face, mouth, and throat that can cause trouble breathing. *GI*: Nausea is the most frequent side-effect of varenicline and is present in approximately 30% of participants taking varenicline (versus 10% of participants taking placebo). The nausea associated with varenicline is generally transient, dose-dependent, of moderate intensity, and leads to dose discontinuation in only 3% (0.6% - 9%) of people who begin taking varenicline. Constipation, flatulence, and vomiting are more rare but possible side-effects. *Sleep complaints*: Insomnia (12% in

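### Surgical outcomes are related to abstinence across any elective operation with no allowance for procedure, so with 20 completers differences between operations may obscure or confound the association

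*Combined protocol and SAP*

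**What the plan says.** - **Who enters.** Section 6: "We will recruit cigarette smokers who have scheduled an elective surgery to participate in the study". The only surgical condition is one of timing: "Inclusion criteria will include having a surgery scheduled 5-10 weeks in advance". No procedure, specialty or inpatient requirement is stated.
- **Where they come from.** Section 5a, Recruitment, is not confined to one service: "We will provide medical departments and physicians detailed information about study eligibility criteria and procedures".
- **Which outcomes.** Objective 2 predicts, with longer abstinence, "shorter length of stay, fewer admissions to the ICU, lower total cost of procedure, smaller total quantity of opioid analgesic use", and fewer 30-day readmissions. The secondary outcomes in Section 8b begin: "These will include length of hospital stay, overall quantity and frequency of opioid analgesic use, pain ratings of during the recovery period". They go on to complications, ICU admission and readmission. Cost is in Objective 2 and in the introduction to Section 8, but not in the 8b list.
- **How they are analysed.** Section 8c: "Surgical outcomes will be evaluated as a function of percent biochemically-confirmed smoking abstinence". The stated purpose is to see whether abstinence is statistically associated with these outcomes. The section opens by saying that "results will be analyzed in a mostly descriptive method". The only covariate named anywhere is medication adherence (Section 7a), and it is optional.
- **What supports the sample size.** Section 8c, Sample Size Considerations, relies on one procedure family: "our pilot data on bariatric patients from FY 2014 included only 23 smokers". Those are the patients of Table 1 in Section 4.

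**The concern.** Days in hospital, dollars, opioid totals and ICU admission depend partly on which operation was done. Table 1 compares smokers with nonsmokers within bariatric surgery, so its contrasts are not mixed with differences between types of operation. The study gives up that restriction and puts nothing in its place.

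Two consequences follow, and they need to be kept apart.

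- **Noise.** Even if procedure is unrelated to abstinence, variation between operations is added to the outcome and weakens any observed correlation. A null result becomes harder to interpret.
- **Confounding.** If participants with larger operations abstain more or less than the others, the association partly reflects the operation. Among 20 people this can happen by chance. It could also be systematic: Section 5a leaves any smoking-based decision on eligibility for surgery to the surgical team, and teams may differ. The documents do not show that such a relation exists.

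At stake are Objective 2 and the opioid part of Objective 3. Section 2 says that a positive signal will support a large grant application. Section 5a also wants to learn whether savings on complications, analgesics and readmissions repay the cost of the study.

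**Working it through.** **1. The plan's own figures.** The 20 completers come with no alpha, power, effect size or SD, so that number can be neither reproduced nor refuted. Two Table 1 figures can be checked.

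- Savings: (34,781.90 − 21,405.19) + (1,364.66 − 520.68) = 13,376.71 + 843.98 = 14,220.69, as stated.
- Readmission, 17% of 23 against 4% of 451: 4/23 against 18/451 gives Fisher p = 0.0172, and 4/23 against 19/451 gives continuity-corrected chi-square p = 0.0177. The stated 0.018 is reproduced.

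**2. How far procedure variance weakens a correlation.** Let k be between-procedure variance divided by within-procedure variance, with procedure unrelated to abstinence. Then:

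- share of outcome variance due to procedure = k/(1 + k)
- observed correlation = within-procedure correlation × 1/√(1 + k)
- effective sample size = 20/(1 + k), which is the same quantity on another scale

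Power uses Fisher's z with n = 20, two-sided alpha 0.05 and a within-procedure correlation of 0.5 (both assumed): Φ(atanh(observed r) × √17 − 1.96). For k = 0.15, observed r = 0.5 × 0.93 = 0.466, atanh = 0.505, 0.505 × 4.123 = 2.08, 2.08 − 1.96 = 0.12, and power is 55%.

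| k (assumed) | Share due to procedure | Correlation factor | Effective n | Power at r = 0.5 |
|---|---|---|---|---|
| 0 | 0% | 1.00 | 20 | 62% |
| 0.15 | 13% | 0.93 | 17.4 | 55% |
| 0.25 | 20% | 0.89 | 16 | 51% |
| 1 | 50% | 0.71 | 10 | 33% |
| 4 | 80% | 0.45 | 4 | 15% |

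With 20 people the critical |r| is 0.44, and 80% power needs r = 0.59 even at k = 0. These formulas suit continuous outcomes. They are not derived for ICU admission, a yes/no event.

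**3. What the documents can say about k.** Table 1 gives no SDs and names no test. Assuming a pooled t-test for length of stay (472 df, p = 0.005, t = 2.82):

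SD = (8.2 − 3.5) / (2.82 × √(1/23 + 1/451)) = 4.7 / (2.82 × 0.214) ≈ 7.8 days.

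If 7.8 days is the within-procedure SD:

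- between-procedure SD of 3 days: k = 9/60.8 = 0.15, share 13%
- between-procedure SD of 5 days: k = 25/60.8 = 0.41, share 29%, factor 0.84
- share of 50%: needs a between-procedure SD of 7.8 days

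If the within-procedure SD were only 2 days (assumed), a between-procedure SD of 3 days gives k = 9/4 = 2.25 and a share of 69%. Stay is probably skewed, so the 7.8 is rough. The share due to procedure can be anything from minor to dominant.

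**The case against.** The strongest reply is that this is a feasibility pilot with a mostly descriptive analysis, that these are secondary outcomes, and that broad enrolment fits the aim of a programme usable in other surgical practices. All of that is true, and it limits the importance of the point. It does not remove it. Section 8c still asks for a statistical association, and the sample-size paragraph claims that 20 completers can show an effect on post-surgical complications. A descriptive display of days or opioid totals over unlike operations is also hard to read.

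A reader might infer four stronger things that the documents do not support.

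- **That the outcomes mainly measure which operation was done.** This needs k above 1. The only pilot figures, under the t-test assumption, suggest wide variation within bariatric surgery itself.
- **That same-day surgery is included.** It is neither included nor excluded. Much of the surrounding text leans towards inpatient operations: the Background speaks of invasive surgery, Section 5a allows healing time before visits resume, and Section 9 expects some rehospitalisations. The share of zero-stay cases is unknown.
- **That outcomes will be analysed on raw scales.** No scale or transformation is stated either way.
- **That a positive result would be uninterpretable because of noise.** Noise weakens a correlation and does not by itself create false positives. Doubt about a positive result needs a relation between procedure and abstinence.

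There are also fair objections to the remedy. Table 1 has no opioid quantity, so its source is not shown to supply procedure-specific opioid values. Ratios to a reference value are unstable for uncommon operations, and splitting 20 people by procedure makes small groups.

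**Conclusion.** The gap is real: a planned association analysis takes no account of an obvious determinant of its outcomes, and the supporting signal is borrowed from a single procedure family. Over the assumed range of k from 0.15 to 4, a true correlation shrinks by a factor of 0.93 to 0.45. Power at 20 is limited before any such loss: 62% for a correlation of 0.5, itself assumed. The documents do not settle where in the range the study will fall, so the supportable word is may: differences between operations may obscure the association, and may confound it if procedure and abstinence are related. The primary outcome, smoking status, is unaffected. The change is worth making because it is cheap and the records are already open to the study team, but it concerns secondary outcomes only.

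**What to change.** In Sections 8b and 8c:

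1. Record the procedure for each participant and whether an overnight stay was planned.
2. Analyse length of stay and total cost relative to the hospital's own mean or median for the same procedure, and opioid quantity likewise where hospital records supply it. Add cost to the 8b list, so that it matches Objective 2.
3. Report length of stay and ICU admission for planned-overnight procedures.
4. List outcomes by procedure family beside the pooled figure.
5. Label the association with abstinence exploratory.

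Enrolment and treatment do not change. The cost is one records extract and a few lines of SAP text; participants must already grant access to their medical records (Sections 5a and 6). There are two downsides: fewer than 20 may contribute to stay and ICU admission, and reference values will be imprecise for uncommon procedures.
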